#### **5.4.1. Liver Chemistry Stopping Criteria**

Liver chemistry stopping and increased monitoring criteria have been designed to assure subject safety and evaluate liver event etiology (in alignment with the FDA premarketing clinical liver safety guidance) [FDA, 2009].

#### 5.4.1.1. Liver Chemistry Stopping and Increased Monitoring Algorithm

➤ If subject to be monitored weekly must refer to Liver Safety Required Actions and Follow up Assessments section in the Appendix

Liver Safety Required Actions and Follow up Assessments Section can be found in [Appendix 12.3](#).

#### 5.4.1.2. Study Treatment Restart or Rechallenge

Study treatment restart or rechallenge after liver chemistry stopping criteria are met by any subject participating in this study is not allowed.

#### 5.4.2. QTc Stopping Criteria

A subject who meets either of the bulleted criteria below will be withdrawn from the study:

- QTc > 500 msec OR uncorrected QT > 600 msec
- Change from baseline of QTc > 60 msec

The QTc is the QT interval corrected for heart rate according to Fridericia's formula (QTcF).

For subjects with underlying **bundle branch block**, follow the discontinuation criteria listed below:

Baseline QTc with bundle branch block	Discontinuation QTc with bundle branch block
< 450 msec	> 500 msec
450 – 480 msec	≥ 530 msec

## 5.5. Treatment interruption

### 5.5.1. Respiratory Symptoms

Study medications will be temporarily suspended to allow investigation in the event of any of the following:

- Persistent reduction in  $D_{LCO} > 15\%$  relative decrease from baseline for three consecutive weeks.
- Persistent cough (CTC grade 2 or 3) or dyspnea (Borg scale grade 3 or above) for three consecutive weeks.

It is recommended that the subject be referred to a pulmonologist for further assessment. The study drug should be suspended until the symptoms or signs that caused referral have resolved and/or the diagnosis has been determined and clinically significant events have been excluded by the pulmonologist. As described in Section 5.4, a confirmed diagnosis of PAP necessitates permanent cessation of study medication and withdrawal of the subject from the study. Suggested pulmonary assessment and management algorithms are provided in a separate Pulmonary Safety Guidance Document in the SRM.

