## 4.2. Treatment Arms and Duration

In the “dose selection” component of the study, subjects will be randomised (1:1:1:1:1) to placebo or one of five subcutaneous GSK3196165 doses, in combination with MTX (at a dose between 15-25 mg previously received for at least 12 weeks, with a stable and tolerated dose and route of administration for  $\geq 4$  weeks).

Treatment with GSK3196165 will be given as a single subcutaneous (SC) injection by an unblinded administrator (shielded to subjects) weekly for 5 injections (Days 1, 8, 15, 22, 29), then EOW thereafter beginning at Day 43 (Week 6).

GSK3196165/placebo must be administered on the same day each week  $\pm 1$  day for the first 5 weekly doses. Following this GSK3196165/placebo must be administered on the same day EOW  $\pm 3$  days.

After the Day 85 (Week 12) administration:

- “Escape therapy” is provided for all subjects not on the 180 mg dose:
  - Subjects in the placebo, 22.5 mg, 45 mg, 90 mg and 135 mg arms will be escalated in a double-blind fashion to the 180 mg (or the highest remaining) dose at Week 14 if they have failed to achieve EULAR good/moderate response\* at Week 12.

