#### 7.4.12. Pulmonary Assessments

Pulmonary assessments are a key aspect of the safety monitoring in this study.

The following pulmonary assessments will be performed at the time points presented in the Time and Events Table (Section 7.1).

- Chest X-ray.
- Cough.
- Borg dyspnea questionnaire.
- Lung auscultation.
- Pulse oximetry.
- Pulmonary function tests (PFTs - spirometry, gas transfer [ $D_{LCO}$ ]).

PFT assessments will be standardized across study sites by the vendor.

In the event of any new or clinically significant pulmonary abnormalities that may develop during the study (e.g., increased shortness of breath/dyspnea, or unexplained and persistent coughing; or >15% relative decrease in DLCO from baseline), it is recommended that the subject be referred to a pulmonologist for further assessment. The study drug should be suspended until the symptoms or signs that caused referral have resolved and/or the underlying diagnosis has been determined and clinically significant events have been excluded by the pulmonologist. Suggested pulmonary assessment/management algorithms are provided in a separate Pulmonary Safety Guidance Document in the SRM.

Additional pulmonary imaging (HRCT) or other tests may be performed on a subject during the study to investigate pulmonary abnormalities, and the DRC or SRT may request copies of any reports or images for central review.

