#### 4.10.5 Respiratory Events

Numbers and percentages of subjects experiencing persistent cough, or persistent dyspnea or persistent DLCO decrease will be reported in a table by actual treatment group at the start time of the event.

Event	Definition
Persistent cough	Cough grade 2 or greater recorded for 3 consecutive weeks (15 or more days) on the eCRF page.
Persistent dyspnea	Borg Scale grade 3 or greater recorded for 3 consecutive weeks (15 or more days) on the eCRF page.
Persistent decrease of D LCO by >15%	Relative decrease of DLCOHCPP of $\geq 15\%$ compared to Baseline for 3 consecutive weeks (15 or more days)

These definitions are provided for guidance to identify potential cases. Final adjudication will be conducted by the SRT.

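### Protocol 5.5.1 and 7.4.12 give different triggers for suspending study drug on the same lung signal, and neither defers to the other

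*Protocol*

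**What the plan says.** Protocol 5.5.1 opens its list of triggers with "Study medications will be temporarily suspended to allow investigation in the event of any of the following". The DLCO item is a fall above 15% that is a "relative decrease from baseline for three consecutive weeks". The symptom item is CTC grade 2 or 3 cough, or "dyspnea (Borg scale grade 3 or above) for three consecutive weeks".

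Protocol 7.4.12 covers a lung abnormality that is either new or clinically significant. Its examples are increased dyspnea, cough that is unexplained and persists, "or >15% relative decrease in DLCO from baseline), it is recommended that the subject be referred to a pulmonologist for further assessment". It continues: "The study drug should be suspended until the symptoms or signs that caused referral have resolved".

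Protocol 4.7.1 attaches the same suspension instruction to pulmonary events of clinical significance, with no threshold or duration. It uses three weekly tests in a row to decide when a DLCO fall is reported as an AESI.

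The dosing instructions in Protocol 6.1 send interruptions to Sections 5.4 and 5.5 and do not mention 7.4.12.

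On escape, Protocol 4.2 says "Subjects in the placebo, 22.5 mg, 45 mg, 90 mg and 135 mg arms will be escalated in a double-blind fashion". The Week 14 step depends on Week 12 EULAR response and the Week 26 step on Week 24 DAS28(CRP). Neither 4.2 nor 6.4 mentions a lung signal.

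SAP 4.10.5 defines the persistent DLCO event as a fall "compared to Baseline for 3 consecutive weeks (15 or more days").

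**The concern.** The plan attaches one action, suspension of study drug, to differently worded triggers. Pulmonary alveolar proteinosis is a named, mechanism-based risk in Protocol 4.7.1, and 7.4.12 treats lung assessments as central to safety monitoring. With about 70 sites expected (SAP 4.9.1.2), the same DLCO result could lead one site to hold the drug and another to give it, each following the protocol. Exposure after a lung signal may then vary by site.

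Timing adds to this. If DLCO is tested at Weeks 12 and 24, a first fall appears two weeks before each escape step. Escalation is blinded and investigators do not see ongoing DAS scores (Protocol 7.3.5), so an investigator with an unconfirmed fall cannot tell whether the next injection is an escalated dose.

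**Working it through.** No power, alpha or sample-size figure is involved. The check is a comparison of text followed by day counting.

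**Text comparison**

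| | Protocol 5.5.1 | Protocol 7.4.12 |
|---|---|---|
| DLCO | >15% relative fall lasting three weeks | >15% relative fall, no persistence |
| Dyspnea | Borg 3 or above for three weeks | increased, no grade or duration |
| Cough | CTC grade 2 or 3 for three weeks | persistent, no grade or stated duration |
| Force | will be suspended | should be suspended, after a recommended referral |
| Reference to the other section | none | none |

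Persistence cannot be assumed for the DLCO example in 7.4.12. The same list attaches persistence to cough, but not to DLCO or dyspnea.

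**Day counting**

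Inputs:
- Week 12 = Day 85, Week 14 = Day 99, Week 24 = Day 169, Week 26 = Day 183 (Time and Events table).
- The every-other-week dosing window is ±3 days (Protocol 4.2).
- Confirmation tests are weekly (Protocol 4.7.1).
- DLCO testing at Weeks 12 and 24 is an assumption, taken from the three-monthly schedule in 4.7.1. The marks for those visits are not readable in the copy of the table used here.

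First fall at Week 12:
- Tests fall on Day 85, 85 + 7 = 92 and 85 + 14 = 99.
- Inclusive span: 99 − 85 + 1 = 15 days, which just meets the SAP count of 15 or more.
- Three elapsed weeks end on Day 85 + 21 = 106.
- The Week 14 dose is on Day 99, window 96 to 102.

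First fall at Week 24:
- Tests fall on Days 169, 176 and 183, and three elapsed weeks end on Day 190.
- The Week 26 dose is on Day 183, window 180 to 186.

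**Doses given under 5.5.1 but withheld under 7.4.12**

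| Circumstances | Doses | Difference |
|---|---|---|
| First result known before dosing; three weekly tests suffice; third result known before the next dose | Day 85 (or 169) | 1 |
| First result known before dosing; three weeks counted as 21 days, or dosing early in the window, or third result late | Days 85 and 99 (or 169 and 183) | 2 |
| First result known only after that day's dose, but before the next | none, or Day 99 (or 183) if one of the conditions in the row above applies | 0 or 1 |

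The Day 99 or Day 183 dose is an escalated dose only if the subject is below the top dose and meets the escape criterion at that visit.

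**The case against.** The best defence is that the two rules can coexist. Section 5.5.1 sets a mandatory floor and does not forbid earlier interruption, while 7.4.12 is a softer step tied to referral. The dosing instructions point to 5.4 and 5.5, which suggests that 5.5.1 is the operative rule. All three lung sections also refer to a Pulmonary Safety Guidance Document, which is not among the documents reviewed and may settle the matter.

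Much of this stands. A reader might infer that a site must suspend under one section and must keep dosing under the other. The text does not support that. The conflict is between *should suspend* and *not required to suspend*. Nor can it be said that sites will diverge, only that they may. But 7.4.12 neither cites nor yields to 5.5.1, and the separate guidance is described as suggested algorithms, so the protocol itself does not resolve the difference.

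A reader might also infer that subjects will receive a first 180 mg dose before a fall can be confirmed. On the nominal schedule the third test falls on the dosing day, and the Time and Events footnotes put safety evaluations before dosing. Section 5.5.1 can therefore suspend in time if three weekly tests suffice and the result is available. Suspension under 5.5 applies at any dose level, so the silence of 4.2 and 6.4 does not override it.

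Finally, a reader might count cough doses given under 5.5.1 against none under 7.4.12. That fails, because 7.4.12 also requires the cough to persist and gives no duration to count from.

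**Conclusion.** The protocol is inconsistent as written. For a first DLCO fall above 15%, or for dyspnea that is increased but ungraded or short-lived, 7.4.12 says to suspend and 5.5.1 does not require it.

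For DLCO the gap is one dose (Day 85 or 169) when that result is known before dosing. It extends to the Day 99 or 183 dose under any of three conditions: 21-day counting, early dosing in the window, or a late third result. If the first result arrives only after that day's dose, the gap can be zero. Lung function results go to a vendor for evaluation (Protocol Appendix 12.7), so same-day availability is itself an assumption, as is DLCO testing at Weeks 12 and 24. Escalation during an open signal is possible but not certain.

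A lesser mismatch lies in SAP 4.10.5, where the DLCO row is labelled >15% but defined as ≥15%. The protocol and SAP 4.10.9 use >15%. A reader might infer that this materially changes event counts. The SAP offers the definition as guidance for finding cases, with final adjudication by the safety review team, so the effect should be small.

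**What to change.** Reconcile Protocol 4.7.1, 5.5.1 and 7.4.12 into one suspension trigger with the same threshold, grade and persistence wording. State how three weeks is counted, and have 7.4.12 refer to 5.5.1. In 4.2 and 6.4, state how an open, unconfirmed lung signal at Week 12 or 24 interacts with escalation at Week 14 or 26. Which trigger applies, and what happens to escalation, is for the sponsor's clinical team to decide. Check the separate pulmonary guidance document against the result.

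As a minor item, make the label and definition in SAP 4.10.5 agree with the protocol and SAP 4.10.9.

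The cost is amended wording in a few protocol sections and one SAP table row. Reconciling the wording needs no new procedure, since weekly confirmation tests are already foreseen in 4.7.1.

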### 5.5.2. Hematologic abnormalities

The following haematological laboratory abnormalities require temporary suspension of study medications and prompt retesting, ideally within 3-5 days:

- White blood cell count  $< 2.0 \times 10^9/L$
- Absolute neutrophil count  $< 1.0 \times 10^9/L$
- Lymphocyte count  $< 0.5 \times 10^9/L$

Study medication should not be restarted until the parameters are above these values, and subjects should be followed as appropriate until resolution of the event.

If these abnormalities are persistent (present on  $\ge 2$  sequential tests), or occur recurrently (on 2 separate occasions), study medications will be permanently discontinued and the subject withdrawn from the study.

## 5.6. Subject and Study Completion

A completed subject is one who has completed all phases of the study including the follow-up visit.

The end of the study is defined as the last subject's last visit.

## 6. STUDY TREATMENT

### 6.1. Investigational Product and Other Study Treatment

The term 'study treatment' is used throughout the protocol to describe any combination of products received by the subject as per the protocol design. Study treatment may therefore refer to the individual study treatments or the combination of those study treatments.

	Study Treatment		Co-medication
Product name:	GSK3196165	Placebo	Methotrexate and folic (or folinic) acid.
Function	Test (investigational product)	Control	Background treatment (started prior to and maintained during the study).
Formulation description:	See IB GSK Document Number [2014N190256_01] for details.	The placebo in this study will be sterile 0.9% (w/v) sodium chloride solution.	Variable. See labels for details.
Dosage form:	Liquid	Liquid	MTX: tablet or liquid Folic (or folinic) acid: capsule, tablet or liquid.
Dosage levels (volumes):	22.5 mg (0.15mL) 45 mg (0.3mL) 90 mg (0.6mL) 135 mg (0.9mL) 180 mg (1.2mL)	0.6 mL	MTX:7.5-25mg/week Folic (or folinic) acid: $\geq$ 5 mg/week. Note: Folic (or folinic) acid dose may be increased to counteract side-effects of MTX (including nausea, mucositis, and headache).
Route of Administration:	Investigational product should be administered SC into thigh or abdomen, sites should be rotated. Safety should be monitored for 1 hour after the injection, for the first 3 injections, then for 30 minutes thereafter. Such monitoring will include general safety monitoring including monitoring for systemic hypersensitivity infusion reactions and local injection site reactions. Trained rescue personnel and rescue medications/equipment must be available for use at all times.		MTX: oral or subcutaneous injection Folic (or folinic) acid: oral

	Study Treatment	Co-medication
Dosing instructions:	
GSK3196165/placebo should be administered on the same day each week <math>\pm</math> 1 day for the first 5 weekly doses (with a minimum of 5 days between doses, for no more than 2 consecutive doses). Following this GSK3196165/placebo should be administered on the same day EOW <math>\pm</math> 3 days (with a minimum of 8 days between doses).
 
GSK3196165/placebo will be discontinued or interrupted as described in Section 5.4 or Section 5.5.
 
Subjects will be randomized as shown in Time and Events Table, Section 7.1, and the dosing schedule should be followed as closely as possible.
 
The unblinded administrator (study co-ordinator or nurse) assigned to the study will be required to prepare and administer the appropriate medication according to the study subject's treatment assignment.
 
Subjects eligible to enter the study will be assigned to treatment randomly through an interactive response technology system (IRTS). Procedures must be in place to ensure the blind is maintained by any site staff involved in clinical care or assessment of the subject, and by the subject themselves.
 
During the first 12 weeks of study every attempt should be made to ensure all doses are administered.
 
After 12 weeks, up to 1 dose in an 8 week period may be missed, not to exceed 2 missed doses total over the 52 weeks of treatment.
 
If at any time the subject misses 2 doses over 52 weeks, the Medical Monitor must be contacted for permission to continue study medication.
	
MTX: can be taken as a single weekly dose, or divided weekly dose, per investigator's discretion.
 
Folic (or folinic) acid should be taken the day after and at least 12 hours following MTX administration.

Physical description:	
Sterile, aqueous solution of purified monoclonal antibody 150 mg/mL
	
Sterile 0.9% (w/v) sodium chloride solution.
 
See label for details

	Study Treatment	Co-medication
Method for individualizing dosage:	
22.5 and 45 mg doses - required volume will be drawn into a small, (e.g. 0.3 or 0.5 mL) syringe.
 
90 and 135 mg doses - required volume will be drawn into a small (e.g. 1 mL) syringe.
 
180 mg dose - required volume will be drawn into a small (e.g. 2 mL or 3 mL) syringe.
 
The required volume should be dosed immediately.
	A volume of 0.6 mL will be drawn into a small (e.g. 1 mL) syringe.

Investigators are responsible for ensuring that subjects continue to receive MTX and folic acid.

Timing of MTX is unrelated to food intake, and may be changed at the investigator's discretion in case of intolerance.

Subjects will receive  $\geq 5$  mg/week folic (or folinic) acid orally. The dosing regimen is at the discretion of the investigator. Folic (or folinic) acid should be taken the day after MTX administration and at least 12 hours following the MTX. Folic (or folinic) acid dose may be increased to counteract side-effects of MTX (including nausea, mucositis, and headache).

MTX dosing should be kept stable throughout the study as far as possible. Dose reduction is permitted to a minimum of 7.5 mg/week due to intolerance or toxicity, and dose increase, following reduction, is permitted back to the subject's dose prior to reduction (maximum dose 25 mg/week). Likewise, temporary interruption of MTX dosing for the management of intolerance will be permitted, and any reduction or interruption should be recorded, with the reason, in the eCRF.

All local standard-of-care practices for the administration of MTX, including laboratory testing, follow-up care, contraindications, and folic acid administration should be performed throughout the study.

## 6.2. Treatment Assignment

Subjects will be assigned to study treatment in accordance with the randomization schedule.

The study will use central randomization and the randomization schedule will be generated by Clinical Statistics using validated randomization software. Once a randomization number has been assigned to a subject, it cannot be assigned to another subject in the study, even if the original subject withdraws before taking study medication.

Randomization numbers will be assigned to subjects using an Interactive Response Technology system (IRTS).

Subjects should be randomized and receive their first dose of study medications on the same day (Day 1).

### **6.3. Planned Dose Adjustments**

This protocol allows some alteration from the currently outlined dosing schedule, but the maximum dose will not exceed 180 mg.

### **6.4. Subject Specific Dose Adjustment Criteria**

- “Escape therapy” is provided for all subjects not on the 180 mg dose:
  - Subjects in the placebo, 22.5 mg, 45 mg, 90 mg and 135 mg arms will be escalated in a double-blind fashion to the 180 mg (or highest remaining) dose at Week 14 if they have failed to achieve EULAR good/moderate response\* at Week 12.
- Subjects in these groups who do not meet this criterion and therefore do not escalate therapy at Week 14 have another opportunity for “escape” at Week 24 with escalation in a double-blind fashion to the 180 mg (or highest remaining) dose of the study after the Interim Analysis) at Week 26 if their DAS28(CRP) score at this timepoint is >3.2.

#### **\*EULAR good or moderate response**

Week 12 DAS28(CRP)	DAS28(CRP) improvement from baseline		
	>1.2	>0.6 and ≤1.2	≤0.6
≤3.2	Good response	Moderate response	No response
>3.2 and ≤5.1	Moderate response	Moderate response	No response
>5.1	Moderate response	No response	No response

Source: [Fransen, 2005]

### **6.5. Blinding**

The study will be double-blind, which means that the investigator and trial staff at site (apart from the unblinded administrator [study co-ordinator or nurse]), subject, and sponsor personnel who are not members of the DRC will be blinded to the trial treatment allocated to each individual subject.

There will be an unblinded administrator (study co-ordinator or nurse) that will prepare and administer the study treatment. A shield (e.g., eye mask or blindfold) will be used during investigational product administration so that subjects are not able to see the

injection volume, syringe size, or any difference in color between GSK3196165 and placebo.

In this Phase 2b study, the DRC (see Section 10.8.1) will have access to unblinded data at a group level, but will not have individual subject level data.

- The investigator or treating physician may unblind a subject's treatment assignment **only in the case of an emergency** OR in the event of a serious medical condition when knowledge of the study treatment is essential for the appropriate clinical management or welfare of the subject as judged by the investigator.
- Investigators have direct access to the subject's individual study treatment.
- It is preferred (but not required) that the investigator first contacts the Medical Monitor or appropriate GSK study personnel to discuss options **before** unblinding the subject's treatment assignment.
- If GSK personnel are not contacted before the unblinding, the investigator must notify GSK as soon as possible after unblinding, but without revealing the treatment assignment of the unblinded subject, unless that information is important for the safety of subjects currently in the study.
- The date and reason for the unblinding must be fully documented in the eCRF

A subject will be withdrawn if the subject's treatment code is unblinded by the investigator or treating physician. The primary reason for discontinuation (the event or condition which led to the unblinding) will be recorded in the eCRF.

- GSK's Global Clinical Safety and Pharmacovigilance (GCSP) staff may unblind the treatment assignment for any subject with an SAE. If the SAE requires that an expedited regulatory report be sent to one or more regulatory agencies, a copy of the report, identifying the subject's treatment assignment, may be sent to investigators in accordance with local regulations and/or GSK policy.

